## **Statistical Analysis Plan**

Prior to hypothesis testing, the data will be examined for normality and outliers. Histograms and values for skewness and kurtosis will be examined. Positively skewed variables will be natural log transformed, unless paired with an excessive number of zeroes. If there are an excess of zeroes in an outcome, the variable will be dichotomized if other values are not well represented, or appropriate modeling techniques will be used (e.g., hurdle models) if other values are well represented. Boxplots will be used to check for outliers. Extreme values will be winsorized (i.e., cases retained in the sample, but values made less extreme). Cases with missing data will be compared to complete cases across major study variables to identify if there are systematic differences in missingness. If significant associations are identified, these variables will be used as covariates in later analyses.

To address Primary Aim 1 of the study, the data will be analyzed using latent growth models within a structural equation modeling framework. Separate models will be conducted for each alcohol outcome: alcohol consumption (e.g., quantity), and alcohol-related problems. It is not known the exact trajectory across time (baseline, 1 month, 3 months, 6 months), so a few models will be compared to identify which best captures the shape of change over time. A simple model that reflects change to 1 month (slope 1; initial change post-intervention) and longer-term maintenance (slope 2; linear growth to 9 months) will be compared to models with additional curvilinear components in case longer-term maintenance is not a linear process. Study condition will be dummy coded with “no booster” as the category of reference, and will serve as a predictor of each latent variable (latent intercept, each slope). All models will be conducted using maximum likelihood estimation, and will control for sex. The model for problems will also control for alcohol quantity.

Given that the tailored feedback boosters address both descriptive drinking norms and protective behavioral strategies, these are considered secondary outcomes. Models identical to the one described above will be conducted (e.g., latent growth models with two slopes, regressed on study condition), but with norms and protective behavioral strategies serving as the outcomes of interest rather than alcohol use or related problems (addressing Primary Aim 2). Given prior findings that emailed booster feedback containing personalized normative feedback and protective behavioral strategies (PBS) was significantly more effective for select groups (i.e., those lower in PBS use [Braitman & Henson, 2016], legal age drinkers [Braitman & Lau-Barraco, 2018]), we will examine potential moderators of booster efficacy as a supplementary exploratory analysis. Legal drinking status by age (coded as 1 = *age 21-24* [legal], 0 = *age 18-20* [underage]) and baseline PBS use (in its original continuous metric) will be explored as potential moderators. The moderator and its interaction with study condition will be added as predictors of each latent factor (latent intercept, slope 1, and slope 2). All models will be conducted in Mplus (version 8; Muthén & Muthén, 1998–2019) using maximum likelihood estimation.

For the Exploratory, Secondary Aim, RSIENA will be used to conduct stochastic, actor-based models (Ripley et al., 2017). These will allow us to examine if behavior change precedes network changes (i.e., selection), or if network changes precede behavior change (i.e., socialization). These models will only be conducted if reductions in drinking or related problems are evidenced in the Primary Aim 1 examination (i.e., there is behavior change over time), and if several members of each organization participate (so network change can be examined over time).

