Thus, the current study has two primary aims (to be examined regardless of study outcomes or participation rates) and an exploratory, secondary aim (to be examined only if the booster is efficacious and the majority of members for each organization enrolled complete the study). Primary Aim 1: We will examine the efficacy of a personalized feedback booster emailed after eCHECKUP TO GO for Alcohol among members of fraternities and sororities. We expect initial post-intervention drinking reductions for both study conditions, with individuals in the booster condition reporting further reductions at later follow-ups. Primary Aim 2: Given the focus on perceived descriptive norms and protective behavioral strategies in the personalized

feedback boosters, we will examine if the booster impacts changes in those constructs over time. We expect individuals in the booster condition will report further reductions in norms and increases in protective behavioral strategies at later follow-ups. Exploratory, Secondary Aim: If the emailed booster is efficacious and the majority of members for each organization enrolled complete the study, we will examine social mechanisms of change (i.e., through selection versus socialization).

Participant population

Eligible participants must 1) be 18 years of age or older, 2) be an undergraduate student at a participating institution; and 3) be a member of a participating fraternity or sorority. Power analyses were conducted using Monte Carlo simulation methods within Mplus (version 5.21, Muthén & Muthén, 2002). Effect sizes, variance, and covariances used were based on data from a preliminary study with a similar protocol (some participants receiving the intervention only, others receiving the intervention plus booster) among college drinkers (Braitman & Henson, 2016; Braitman & Lau-Barraco, 2018). We estimated a retention rate of 76%, the average reported in a meta-analysis of RCTs assessing alcohol interventions for first-year college students (Scott-Sheldon et al., 2014). Monte Carlo simulation methods indicated that for the effect size expected ($b = 6.57$, $\beta = 0.537$) and for the expected 24% attrition, a sample size of $N = 180$ total students should yield sufficient power (.80+) to detect booster effects.

Recruitment Procedure

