Boosters: After the intervention, participants receive additional emails from the researcher, depending on their study condition. For the intervention-plus-booster study condition, these emails contain personalized normative feedback about alcohol use as well as feedback about harm reduction strategies, serving as a booster to the original intervention. Baseline data are used to provide students with normative information (e.g., typical drinking among ODU students who are male/female), and reminders of protective behavioral strategies they can use to reduce drinking-related harm (separated by strategies they have reported using recently versus those they might consider trying). This is received at 2 weeks, 6 weeks, 10 weeks, and 14 weeks after baseline. Participants in the intervention-only control condition do not receive any feedback via email. Participants are assigned to study condition at the group level, so that an entire organization receives the booster emails (or the entire organization does not).

Measures

The same measures are included in baseline and the follow-up surveys:

Participants' **alcohol use** is assessed using a modified version of the Daily Drinking Questionnaire for the past 30 days (Collins et al., 1985). Additionally, participants describe specific aspects regarding their drinking in the past 30 days (e.g., highest consumption in a single day). **Descriptive Norms** are assessed by modifying the DDQ to reflect their expectations for typical male students at the same institution, typical female students at the same institution, and

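### The booster effect may be split between slope 1 and slope 2, and the SAP plans no estimate of the arm difference in change from baseline at the later follow-ups

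*SAP*

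**What the plan says.** The Protocol (Study Procedure, Boosters) gives the schedule for the booster arm: "This is received at 2 weeks, 6 weeks, 10 weeks, and 14 weeks after baseline". For the other arm it says: "Participants in the intervention-only control condition do not receive any feedback via email". Both arms complete eCHECKUP TO GO at the baseline session. Under Primary Aim 1 the Protocol states the hypothesis: "We expect initial post-intervention drinking reductions for both study conditions, with individuals in the booster condition reporting further reductions at later follow-ups".

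The SAP (Primary Aim 1 models) begins with "A simple model that reflects change to 1 month (slope 1; initial change post-intervention" and a second, linear slope for the period up to the last wave, to be compared with curvilinear alternatives. Study condition "will serve as a predictor of each latent variable (latent intercept, each slope". The same structure is used for norms and protective strategies under Aim 2.

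The SAP text available for review names no combined contrast, no model-implied arm difference at 3 months or the last wave, no joint test of the slope coefficients, and no rule for reading the two slope results together. The slope loadings are not given.

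**The concern.** The hypothesis concerns benefit at the later follow-ups, whereas the planned output is two coefficients covering two consecutive periods. Booster exposure falls in both periods. If the effect builds across both, each slope test sees only part of it. If an early effect is held, the slope 2 coefficient is zero. If it partly fades, the slope 2 coefficient changes sign although the booster arm has still reduced more since baseline.

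A reader could add the two coefficients by hand, but could not form a confidence interval for the sum without their covariance, which is not a planned output. A contrast chosen after seeing which slope is significant is also weaker evidence than one named in advance. The Protocol makes the exploratory network aim depend on the booster being efficacious, so how the slopes are read has a consequence beyond Aim 1.

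**Working it through.** **Timing.** One month is week 4.35, so 1 of 4 boosters precedes the first follow-up. Three months is week 13.04, so 3 of 4 precede the second, and the week-14 booster comes after it. All 4 precede a last wave at 6 or 9 months. Alcohol use is asked for the past 30 days, so about 30 − 14 = 16 of the 30 days reported at 1 month follow the first booster. An early arm difference is possible, but not certain.

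**The missing quantity.** Let g1 and g2 be the condition coefficients on slope 1 and slope 2. Assume slope 1 is loaded 0, 1, 1, 1 and slope 2 is loaded 0, 0, 2, T−1, with T the last wave in months. The arm difference in change from baseline at month t (1 or later) is then

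D(t) = g1 + (t−1) × g2.

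This is g1 at 1 month, g1 + 2 × g2 at 3 months, and g1 + 5 × g2 at 6 months or g1 + 8 × g2 at 9 months. If slope 2 is instead loaded 0, 1, 3, T, it becomes D(t) = g1 + t × g2. The weights change and the point stands.

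**Reversed slope 2.** With reductions negative, take g1 = −.30 SD and D(T) = −.20 SD. Then g2 = (−.20 + .30)/5 = +.02 SD per month for T = 6, or .10/8 = +.0125 for T = 9. Slope 2 favours control while the booster arm is still better.

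**The plan's own figure.** The Protocol (Participant population) gives N = 180 for power of at least .80, with b = 6.57, β = 0.537 and 24% attrition. It does not say which coefficient this is, and the simulation variances and covariances are not given, so the figure cannot be reproduced. Read as a simple two-group difference in SD units, .537 needs 110 completers, or 110/.76 = 145 enrolled, for 80% power. At 180 enrolled the power is .88, which is consistent with the statement but does not confirm it. The present point does not depend on it.

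**Illustration.** Assumptions: total effect .537 SD at the last wave; 180 × .76 ≈ 137 analysed, 68.5 per arm; unit variance with equal correlation .6 between waves; no clustering; T = 6; two-sided .05. Generalized least squares for the arm difference gives:

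- SE(g1) = .1435
- SE(5 × g2) = .1518
- correlation of the two estimates −.49
- SE of the sum = √(.1435² + .1518² − 2 × .49 × .1435 × .1518) ≈ .149

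Power is Φ(effect/SE − 1.96).

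| Course of the effect | Slope 1 | Slope 2 | Total at 6 months |
|---|---|---|---|
| None by 1 month | .05 | .537/.1518: .94 | .537/.149: .95 |
| A quarter by 1 month | .16 | .403/.1518: .76 | .95 |
| Half by 1 month | .2685/.1435: .46 | .2685/.1518: .42 | .95 |
| All by 1 month, held | .96 | .05 | .95 |
| All by 1 month, half lost by 6 months | .96 | wrong sign | .2685/.149: .44 |

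For the even split, the chance that either slope is significant is .77, with type I error .09. The joint 2-df test has .91. Over correlations .4 to .7 the even-split ranges are .33–.58 for slope 1, .30–.53 for slope 2 and .84–.99 for the total.

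**Sensitivity to the covariance structure.** The SAP makes the slopes latent variables, so slope variance is the natural case and equal correlation a special one. With random slopes (intercept variance .5–.6, slope 1 variance 0–.3, slope 2 variance .01–.02, residual .4) and T = 6, power for the total falls to about .71–.88. Neither slope test gains power in these cases.

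**Interval without the covariance.** Under equal correlation, √(.1435² + .1518²) = .209, and .209/.149 = 1.40, so the interval is 40% too wide. With the random-slope structures above or the AR(1) structures tried, it is about 4–32% too wide at 6 months.

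**Final wave.** Take g1 = .2685 and g2 = .0537 per month in absolute value. Then .2685 + 5 × .0537 = .54 SD, and .2685 + 8 × .0537 = .70 SD. The Protocol's Study Procedure gives 6 months, its subsequent-assessments paragraph gives 9, and the SAP gives both.

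**The case against.** The best defence is that the model fits its hypothesis. The Protocol expects a shared early drop and a later booster advantage. Slope 1 captures the first, slope 2 the second, and condition predicts both. The wanted figure is a linear combination of coefficients from the same fitted model, so nothing is biased or beyond estimation. The documents support no particular split of the effect. After one of four boosters, half by 1 month is unfavourable to the plan, and at a quarter slope 2 still has .76. Nobody proposes to combine the standard errors without their covariance.

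All of this stands. It limits the point to an added estimate, but it does not say how the results are to be read if the effect is split, held or fading.

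A reader might infer more, and three stronger readings fail:

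- **Slope 1 is contaminated by the response to the online program.** Both arms complete it and controls get no emailed feedback, so that response cancels in the arm difference.
- **The trial is underpowered for Aim 1.** The Protocol does not say which coefficient .537 is. If it is the slope 2 effect, slope 2 has .94 in the illustration.
- **The baseline contrast should replace the slope tests.** When an early effect fades by half, the final-wave contrast has .44 and slope 1 has .96.

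**Conclusion.** The point holds as a modest gap in the planned estimates, worth considering. The week-2 booster falls inside slope 1, condition is tested on each slope separately, and no planned estimate gives the arm difference in change from baseline at the follow-ups where benefit is expected.

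The cost depends on an unknown time course. It is large for an even split, moderate if a quarter comes by 1 month, and nil or nearly so if the whole effect falls in one period. The power figures rest on the assumed effect, correlation, covariance structure and loadings. They ignore assignment by organization, so the absolute levels are optimistic. The 40% interval figure belongs to the equal-correlation structure only.

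**What to change.** Keep the model and both slope tests, and add the following to the SAP:

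- **Final wave.** Reconcile 6 and 9 months first, because the weight on slope 2 depends on it.
- **Loadings.** State them for both slopes.
- **Contrast.** For the Aim 1 and Aim 2 models, prespecify the model-implied arm difference in change from baseline, with confidence interval, at 1 month, 3 months and the final wave. Form it in MODEL CONSTRAINT from the loadings actually used: g1 + (t−1) × g2 for slope 2 loaded 0, 0, 2, T−1, or g1 + t × g2 for 0, 1, 3, T, plus any curvilinear term selected.
- **Reading.** Label it a supporting estimate. State that a null or reversed slope 2 is not by itself read as no efficacy. If one overall test is wanted, use the joint test of condition on all slopes.
- **Scale.** The SAP says "Positively skewed variables will be natural log transformed, unless paired with an excessive number of zeroes", and for excess zeroes that "appropriate modeling techniques will be used (e.g., hurdle models) if other values are well represented". Name the scale or model part to which the contrast refers.
- **Problems outcome.** Since "The model for problems will also control for alcohol quantity", label that contrast as adjusted for quantity, or also report it unadjusted if the total effect is wanted.

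The cost is SAP wording and a few lines of syntax per model, with no new data. Four outcomes at three times make 12 estimates. About 8 are new, because with the first loading the 1-month value is already the slope 1 coefficient. With the second loading all 12 are new. There are more if norms for male students, female students and close friends are modelled separately, or if problems is also reported unadjusted. None should be presented as an extra efficacy test.

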An email is sent to presidents of fraternities and sororities at the participating institutions. We explain the purpose and design of the study, share relevant approvals (IRB, NIH Certificate of Confidentiality, etc.), and explain the benefits of participation, including monetary compensation. Presidents who opt in for their chapter's participation share membership lists (names and email addresses). Names on membership lists are used for social network assessment in each survey (described in more detail in the Measures section below). Research staff then send recruitment emails to all members in participating organizations. This email contains similar content as the email sent to chapter presidents (i.e., study purpose and design, relevant approvals, compensation structure). We also ask chapter presidents if we may attend a chapter meeting to describe the study in more detail and answer questions. Some but not all organizations have chosen to do this so far. Undergraduate research assistants who are also members of Greek life make these visits. Recruitment emails include a link to Calendly to schedule their participation for the baseline session via Zoom.

Study Procedure

Members of Greek life are recruited via email as described above. Participants schedule their participation time through an online time management system (Calendly). They receive an email reminder from the Calendly system 24 hours before their assigned timeslot. After participating in the fully remote baseline session via Zoom, participants are to be paid \$20. Participants are invited to complete additional 1-, 3-, and 6-month assessments, and receive \$5 for each completed follow-up survey. As an additional incentive, participants who complete all assessments will be given a \$5 bonus (yielding a \$40 total for the study if all follow-ups are completed). All monetary compensation is provided via online gift card to Amazon.

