Baseline: Participants sign on to Zoom via the link provided during their assigned timeslot. Upon signing into the Zoom meeting, the research assistants provide a link (using the chat function) directing them to a Qualtrics survey. Participants read and view videos of the study procedures on the first page of this website. The videos have been created in Powtoon, using voiceover and images that are not related to a specific gender or race/ethnicity. After reviewing the videos, participants are provided with the informed consent document (on a subsequent page of the survey), and will have the opportunity to ask questions during the live Zoom session with the research assistant. After consenting to participate, they are directed to complete the baseline survey (approximately 30-45 minutes). All participants will complete this computerized survey that assesses alcohol use, alcohol-related problems, protective behavioral strategies for drinking and their perceived effectiveness, alcohol-related cognitions (motives, expectancies, and beliefs about alcohol use), social network characteristics, cannabis and tobacco use, COVID-19 pandemic experiences, internalizing symptoms, and demographic measures. After completing the initial assessment, participants are then be directed to navigate through the eCHECKUP TO GO program (San Diego State University Research Foundation, 2018) until it is completed (approximately 20-30 minutes).

Subsequent assessments: Approximately 1, 3, and 9 months after the initial assessment, researchers send each participant an email reminding them to complete the follow-up assessment. This email includes a link to an online follow-up survey that assesses alcohol use, related problems, protective behavioral strategies for drinking and their perceived effectiveness, social network characteristics, and cannabis and tobacco use. If participants provide additional ways to contact them during the baseline survey (a second email address, a phone number to text), these methods are also used to send the link to the follow-up surveys.

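### Start term is in neither the described assignment nor the growth models, so a chance imbalance in chapter start dates can enter the booster effect, and average early change cannot be separated from season

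*SAP*

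**What the plan says.** **Entry.** Protocol, Recruitment Procedure: "Presidents who opt in for their chapter's participation share membership lists (names and email addresses"). Members then book their own session: "Participants schedule their participation time through an online time management system (Calendly"). No common start date or enrolment window is given. On visits to chapter meetings, the same section says "Some but not all organizations have chosen to do this so far", so recruitment was in progress in a protocol dated July 7, 2022.

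**Timing.** Protocol, Study Procedure, opening paragraph: "Participants are invited to complete additional 1-, 3-, and 6-month assessments". The same section, under Subsequent assessments: "Approximately 1, 3, and 9 months after the initial assessment, researchers send each participant an email". The SAP lists occasions to 6 months but describes the growth model as follows: "A simple model that reflects change to 1 month (slope 1; initial change post-intervention) and longer-term maintenance (slope 2; linear growth to 9 months"). The 6- and 9-month statements must be reconciled, because they decide which calendar months slope 2 covers.

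**Outcome.** Protocol, Measures: alcohol use comes from a "modified version of the Daily Drinking Questionnaire for the past 30 days".

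**Assignment.** Protocol, Boosters: condition is assigned to whole organizations. No method, ratio, blocking or stratification is described. All participants complete eCHECKUP TO GO; controls lack only the emailed boosters.

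**Models.** SAP: condition predicts the intercept and each slope, with sex as covariate and quantity added in the problems model. Other covariates enter only if they are associated with missingness. Moderators are legal drinking age and baseline protective strategies. Term, month, cohort and start date are not mentioned, and neither is chapter.

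**Expectation.** Protocol, Primary Aim 1: "We expect initial post-intervention drinking reductions for both study conditions".

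**The concern.** Each survey measures about one month of an undergraduate's year. Which month it is depends on when the person, and largely the chapter, started. Counting 1, 3, 6 and 9 months from a September baseline gives October, December, March and June; from a February baseline it gives March, May, August and November. If drinking differs between term and break, the same growth model fitted to these two groups would show different slopes with no booster effect at all.

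Two results are exposed, to different degrees.

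- **Booster contrast (conditional).** If start terms are unevenly split between arms, part of the seasonal difference appears as a condition effect on the slopes. Start term mostly belongs to the chapter, which is the unit assigned, so enrolling more students per chapter does not average it out.
- **Average early change (direct).** Everyone receives eCHECKUP TO GO, so a fall by 1 month in both arms has no untreated comparator, and a shared seasonal fall passes one-for-one into slope 1. The SAP opens the network analysis if Aim 1 shows reductions over time, so season alone could meet that condition. The protocol's Primary Aims section instead requires the booster to be efficacious.

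**Working it through.** **1. The plan's own figure.** Inputs from Protocol, Participant population: b = 6.57, β = 0.537, 24% attrition, N = 180, power .80+. The plan used a growth-model simulation whose variances are not given, so only consistency can be checked. Treat β as a standardized mean difference, with two-sided alpha 0.05 and 1:1 allocation (both assumed):

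- n per arm = 2(1.960 + 0.842)² / 0.537² = 54.4, so 55; total 110; 110/0.76 = 145 after rounding up.
- With 180 × 0.76 = 136.8 retained, 68.4 per arm: power = Φ(0.537 × √(68.4/2) − 1.960) = Φ(1.18) = 0.88.

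This agrees with .80+. The present point does not show N = 180 to be wrong. About 137 completers are carried forward.

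**2. Bias for a given imbalance.** Let s be the difference in change between two start terms, in SD, and p_B and p_C the shares of each arm starting in one of them. Then

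bias in the condition effect = s × (p_B − p_C).

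| s (assumed) | imbalance (assumed) | bias | share of β = 0.537 |
|---|---|---|---|
| 0.25 | 0.25 | 0.06 SD | 12% |
| 0.5 | 0.25 | 0.125 SD | 23% |
| 0.5 | 0.50 | 0.25 SD | 47% |
| any | 0 | 0 | 0% |

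**3. How likely imbalance is by chance.** The chapter count is not stated. Assume 8 equal chapters, 4 starting in each of two terms, and 4 per arm by unrestricted random assignment. The number of booster chapters from one term is hypergeometric, with weights 1, 16, 36, 16, 1 out of 70.

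- No imbalance: 36/70 = 51%.
- 3:1 or worse: (32 + 2)/70 = 49%.
- Mean absolute imbalance: (32 × 0.5 + 2 × 1)/70 = 18/70 = 0.257. The same sum gives 72/252 = 0.286 for 10 chapters and 200/924 = 0.216 for 12.
- The signed imbalance averages zero. Its mean square with 8 chapters is (32 × 0.25 + 2 × 1)/70 = 1/7, so its SD is 0.38.

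So random assignment gives zero expected bias and added chapter-level variance. At s = 0.5 the added SD is 0.5 × 0.38 = 0.19, about the size of the student-level standard error of 2/√137 = 0.17.

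**4. Type I error.** Null simulation of a two-arm comparison of change: 137 completers, equal chapters, two start terms, no other clustering, 4,000 runs per cell. This stands in for the growth model; it does not refit it. Analysis ignoring both chapter and term:

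| Chapters | s = 0.25 | s = 0.5 | s = 1.0 |
|---|---|---|---|
| 4 | 0.13 | 0.30 | 0.35 |
| 8 | 0.10 | 0.19 | 0.41 |
| 12 | 0.07 | 0.14 | 0.30 |
| 20 | 0.07 | 0.10 | 0.20 |

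With s = 0 the error is about 0.05. For s > 0, adding start term as a covariate gives 0.046 to 0.061 wherever it can be estimated. Assignment stratified by term plus the covariate gives 0.040 to 0.056. With 4 chapters, arm and term coincide completely in 2 of 6 draws; those draws cannot be adjusted and are left out of the covariate figures.

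**5. In drinks.** If b is in drinks and β = b/SD, the SD is 6.57/0.537 = 12.2. An assumed seasonal difference of 2 to 4 drinks is then 0.16 to 0.33 SD, nearest the s = 0.25 column. With 8 chapters the mean imbalance gives 0.257 × 2 to 0.257 × 4 = 0.5 to 1.0 drinks (8% to 16% of 6.57). A 3:1 split gives 1 to 2 drinks (15% to 30%).

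**The case against.** **Staggered starts are inferred.** The phrase about progress so far concerns visits to chapter meetings. It shows ongoing recruitment, not that chapters began in different terms. This stands: entry across terms is likely but not shown, and if all chapters started in one term the booster contrast has no such bias.

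**Silence is not a finding about assignment.** A reader might infer that assignment ignored recruitment period. The documents describe no method at all, so they do not support that.

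**It is mainly a clustering problem.** This largely stands. Under random assignment, season adds between-chapter variance. In the same null setting, a plain chapter-level t-test with no calendar variable gave type I error of 0.055, 0.052 and 0.049 for 8, 12 and 20 chapters at s = 0.5. It did not rescue 4 chapters (0.12). Accounting for chapter is therefore the primary repair where chapters are not very few. Start term then mainly adds precision and removes the imbalance in the trial actually run.

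**Members of a chapter do not share one window.** Each person books a slot, so windows spread within a chapter. The shared shift is partial, which makes the figures above upper-end for a given s.

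**Slope 1 is only a label.** A reader might infer that the plan will claim efficacy for eCHECKUP TO GO. The SAP specifies no such test; its label for slope 1 is temporal, and Aim 1 concerns the booster. That stands, but the stated expectation of reductions in both arms and the SAP's condition for the network analysis leave room for the attribution.

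**A term/break indicator may not be estimable.** If starts cluster, it is nearly collinear with survey wave and competes with slope 2 and the curvilinear terms. This stands and limits its role to a sensitivity analysis.

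**Conclusion.** The point holds as a conditional weakness with a cheap remedy. Nothing in the described assignment or in the SAP models protects the booster contrast from a chance imbalance in start term. The planned model also names no chapter term that would carry the resulting variance into the standard error. Under random assignment the expected bias is zero; the harm is inflated type I error and an unremoved imbalance in the realized trial.

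The size is unknown. The figures rest on an assumed number of chapters (4 to 20), two equal start terms, a seasonal difference of 0.25 to 1.0 SD, equal arms and alpha 0.05. None of these is in the documents.

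A reader might infer that season has biased the booster effect, or that the bias is 1 to 2 drinks. The documents support neither. They do not show that an imbalance occurred, and that range needs both an assumed swing and a 3:1 split, when 51% of draws with 8 chapters have no imbalance.

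The statement about average slope 1 needs no such assumptions: without an untreated arm it cannot be separated from season.

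**What to change.** 1. **Assignment.** Assign chapters not yet assigned in blocks within recruitment term, and state the method used for those already assigned.
2. **Models.** Add start term as a predictor of each slope in the Aim 1 and Aim 2 models, alongside an analysis that accounts for chapter. Keep a time-varying indicator of whether each 30-day window fell in term or break as a sensitivity analysis, used only where start dates are staggered enough to estimate it.
3. **Interpretation.** State that average slope 1 is descriptive change after eCHECKUP TO GO, that efficacy conclusions rest on the condition contrast, and that meeting the change-over-time condition for the network analysis does not attribute that change to the intervention.
4. **Schedule.** Reconcile the 6- and 9-month statements, so that the calendar months behind slope 2 are defined.

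**Cost.** SAP wording, a variable derived from baseline dates, a blocking rule and one more parameter per slope. If arm and term are fully confounded among a few chapters, the covariate cannot separate them. Only blocking the remaining chapters helps there; otherwise the limitation must be reported. If all chapters started in one term, item 2's covariate drops out at no loss.
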